9.6 Statistical Methods

Statistical testing and inference for safety analyses are described in Section 9.6.2. Efficacy results that will be deemed to be statistically significant after consideration of the Type-1 error control strategy are described in Section 9.8. Nominal p-values and 90% CIs will be computed for other efficacy analyses but should be interpreted with caution due to potential issues of multiplicity, sample size, etc.

9.6.1 Statistical Methods for Efficacy Analysis

This section describes the statistical methods that address the primary and secondary objectives. Methods related to exploratory objectives will be described in the sSAP.

The treatment regimen intended for evaluation of the primary efficacy objectives is the randomized treatment administered as add-on therapy to stable antidepressant therapy as directed. For the MK-1942 daily dose group, this will include dose modification allowed for intolerability or non-adherence at or after 2 weeks of treatment with primary evaluation after 3 weeks of therapy. For the MK-1942 intermittent dose group, the primary evaluation will be after 1 week of therapy. The primary analysis strategy (HS) will exclude data collected after discontinuation of study intervention or stable antidepressant therapy, initiation of a non-study antidepressant therapy or premature unblinding of either the investigator or participant. A supplemental analysis strategy (TPS) will also be evaluated in which data collected after these intercurrent events will be included.

A single statistical model including data from all 3 treatment groups through Week 4 will be used to contrast the treatment comparisons/timepoints of interest for each of the primary and secondary efficacy endpoints. The primary analysis is based on a longitudinal ANCOVA

model including calculated change from baseline at Week 1, Week 2, Week 3, and Week 4. The model will handle missing data (both intermittent missing and monotone missing due to dropout) using the missing at random assumption. This model will be used to generate confidence intervals and p-values (compared with placebo). This model assumes a different mean for each treatment at each of the repeated time points in the analysis. In this model, time is treated as a categorical variable so that no restriction is imposed on the trajectory of the means over time. The analysis model will include categorical terms for treatment, number of treatment failures (1; >1) for the current episode of moderate-to-severe MDD, and week, as well as a continuous term for baseline response. In addition, the model will also include the interaction terms of week-by-treatment and week-by-baseline response. The treatment difference in terms of the mean change from baseline at a given time point will be estimated, and as appropriate, tested from the model. An unstructured covariance matrix will be used to model the correlation among repeated measurements. The Kenward-Roger approximation will be used to compute the degrees of freedom [Kenward, M. G. and Roger, J. H. 1997]. A sensitivity analysis will be performed for the primary and key secondary hypotheses to assess the robustness of the primary findings with respect to the handling of missing data. Specifically, a control-based mean imputation approach, with a tipping-point component, will be applied [Mehrotra, D. V., et al 2017]. Details related to this sensitivity analysis will be provided in the sSAP.

As outlined in Table 6, supportive analyses will be performed for the primary and the key secondary hypotheses to assess the robustness of the primary findings with respect to (1) the impact of intercurrent events; and (2) the handling of missing data. Details related to supportive analyses will be provided in the sSAP.

Basic summary statistics will be computed for all efficacy endpoints over time. This minimally includes means and standard deviations for continuous-type endpoints and counts and percentages for categorical endpoints.

Table 6 summarizes the key efficacy analyses.

PROTOCOL/AMENDMENT NO.: 006-03

Table 6 Analysis of Key Efficacy Variables

Endpoint/Variable (Description, Time Point)	Primary vs. Supportive Approach ^a	Statistical Method ^b	Analysis Population	Missing Data Approach	
Primary Hypotheses					
	Р	Longitudinal ANCOVA ^c with HS estimand	FAS	Model-based ^d	
Change from baseline at Week 3 in MADRS total score (MK-1942 daily dose versus placebo)	S	Longitudinal ANCOVA with HS estimand and Control-Based Mean Imputation ^c	FAS	Control-based mean imputation	
	S	Longitudinal ANCOVA ^c with TPS estimand	FAS	Model-based ^d	
	P	Longitudinal ANCOVA ^c with HS estimand	FAS	Model-based ^d	
Change from baseline at Week 1 in MADRS total score (MK-1942 intermittent dose versus placebo)	S	Longitudinal ANCOVA with HS estimand and Control-Based Mean Imputation ^c	FAS	Control-based mean imputation	
	S	Longitudinal ANCOVA ^c with TPS estimand	FAS	Model-based ^d	
	Seco	ndary Hypotheses			
	Р	Longitudinal ANCOVA ^c with HS estimand	FAS	Model-based ^d	
Change from baseline at Week 3 in HAM-D17 total score (MK-1942 daily dose versus placebo)	S	Longitudinal ANCOVA with HS estimand and Control-Based Mean Imputation ^c	FAS	Control-based mean imputation	
	S	Longitudinal ANCOVA ^c with TPS estimand	FAS	Model-based ^d	
	P	Longitudinal ANCOVA ^c with HS estimand	FAS	Model-based ^d	
Change from baseline at Week 1 in HAM-D17 total score (MK-1942 intermittent dose versus placebo)	S	Longitudinal ANCOVA with HS estimand and Control-Based Mean Imputation ^c	FAS	Control-based mean imputation	
	S	Longitudinal ANCOVA ^c with TPS estimand	FAS	Model-based ^d	

C Confidential

Endpoint/Variable (Description, Time Point)	Primary vs. Supportive Approach ^a	Statistical Method ^b	Analysis Population	Missing Data Approach
	P	Longitudinal ANCOVA ^c with HS estimand	FAS	Model-based ^d
Change from baseline at Week 3 in CGI-S (MK-1942 daily dose versus placebo)	S	Longitudinal ANCOVA with HS estimand and Control-Based Mean Imputation ^c	FAS	Control-based mean imputation
	S	Longitudinal ANCOVA ^c with TPS estimand	FAS	Model-based ^d
	P	Longitudinal ANCOVA ^c with HS estimand	FAS	Model-based ^d
Change from baseline at Week 1 in CGI-S (MK-1942 intermittent dose versus placebo)	S	Longitudinal ANCOVA with HS estimand and Control-Based Mean Imputation ^c	FAS	Control-based mean imputation
	S	Longitudinal ANCOVA ^c with TPS estimand	FAS	Model-based ^d

ANCOVA=Analysis of covariance, CGI-S=Clinical Global Impression-Severity; FAS=full analysis set, HAM-D17=17-item Hamilton Depression Rating Scale; HS=hypothetical strategy; MADRS=Montgomery-Asberg Depression Rating Scale; MDD= major depressive disorder; TPS=treatment policy strategy

- ^a P=Primary approach, S=Supportive approach
- ^b Statistical models are described in further detail below.
- Longitudinal data analysis model with terms for treatment, number of treatment failures (1 treatment failure;
 1 treatment failure [for the current episode of moderate-to-severe MDD]), week, and baseline response. In addition, the model will also include the interaction terms of week-by-treatment and week-by-baseline response.
- d Imputation for missing items as noted in Section 9.4.4 will be conducted prior to using this model-based approach.

The strategy to address multiplicity issues with regard to multiple efficacy endpoints and an interim analysis is described in Section 9.7 (Interim Analyses) and in Section 9.8 (Multiplicity), respectively.

9.6.2 Statistical Methods for Safety Analysis

Safety and tolerability will be assessed by clinical review of all relevant parameters including AEs, laboratory tests, vital signs, and ECG measurements.

The analysis of safety results will follow a tiered approach (Table 7). The tiers differ with respect to the analyses that will be performed. AEs (specific terms as well as system organ class terms) and events that meet PDLC criteria in laboratory, vital signs, and ECG parameters are either prespecified as "Tier 1" endpoints, or will be classified as belonging to "Tier 2" or "Tier 3" based on the number of events observed.

PRODUCT: MK-1942

PROTOCOL/AMENDMENT NO.: 006-03

Tier 1 Events

Safety parameters or AEs of special interest that are identified *a priori* constitute "Tier 1" safety endpoints that will be subject to inferential testing for statistical significance. There are no Tier 1 events for this protocol as the evaluation of safety and tolerability is focused on estimating rather than testing treatment differences and the incidence of AEs of special interest is anticipated to be rare.

Tier 2 Events

Membership in Tier 2 requires that at least 7% of participants (corresponding to at least 4 participants in the MK-1942 daily dose group, 2 participants in the MK-1942 intermittent dose group, and 4 participants in the placebo group) in any treatment group exhibit the event. The threshold of at least 7% was chosen because the 95% confidence interval for the between-group difference in percent incidence will always include zero when treatment groups of equal size each have less than 4 events (and when a treatment group of half-allocation has less than 2 events) and thus would add little to the interpretation of potentially meaningful differences. Because many 95% confidence intervals may be provided without adjustment for multiplicity, the confidence intervals should be regarded as a helpful descriptive measure to be used in review, not a formal method for assessing the statistical significance of the between-group differences in adverse events and safety parameters that meet predefined limits of change.

In addition to individual events that occur in 7% or more participants in any treatment group, the broad AE categories consisting of the proportion of participants with any AE, a drug-related AE, a serious AE, an AE which is both drug-related and serious, and discontinuation due to an AE will also be considered Tier 2 endpoints.

Dizziness AEs of moderate or severe intensity and gait disturbance independent of feelings of dizziness AEs are Tier 2 AEs.

Tier 3 Events

Safety endpoints that are not Tier 2 events are considered Tier 3 events. Only point estimates by treatment group are provided for Tier 3 safety parameters.

Categorical Safety Measures

C-SSRS

The percentage of participants with any treatment-emergent suicidal ideation or with any treatment-emergent suicidal behavior will be analyzed per the tiered analysis strategy outlined above, and will be considered as either Tier 2 or Tier 3 events, depending on the number of participants with an event observed within each treatment group. Additionally, the 11 prespecified categories of suicidal ideation and behavior will be summarized. Participant counts (and cumulative counts) for each category will be based upon the most severe treatment-emergent event observed during the assessment period.

In constructing the treatment-emergent C-SSRS analyses, a pretreatment reference period is required, from which a baseline score for each of the 3 categories (ideation, behavior, nonsuicidal self-injury) is derived. For this study, the baseline score for each of the 3 categories will be taken as the maximum score arising from the 3 predose C-SSRS administrations. The first predose administration references lifetime history. Each subsequent predose administration references the timeframe since the last predose administration.

It is noted that the first predose administration actually consists of 2 separate administrations; 1 using lifetime as the reference period and another using fixed-time intervals (6 months for behavior and 2 months for ideation). The fixed-time administration is solely included for inclusion/exclusion purposes (noting that the contemporaneous maximum lifetime baseline score may not be less than the maximum fixed-time baseline score by definition).

Continuous Safety Measures

For continuous measures such as changes from baseline in laboratory, vital signs, and ECG parameters, summary statistics for baseline, on-treatment, and change from baseline values will be provided by treatment group in table format.

Table 7 summarizes the safety analysis.

Table 7 Analysis Strategy for Safety Parameters

Safety Tier	Safety Endpoint	p-value	95% CI for Treatment Comparison	Descriptive Statistics
Tier 2	Any AE		X	X
	Any Serious AE		X	X
	Any Drug-related AE		X	X
	Any Serious and Drug-related AE		X	X
	Discontinuation due to an AE		X	X
	Specific AEs, SOCs, or PDLCs (incidence ≥7%) of participants in 1 of the treatment groups)		X	X
	Dizziness AEs of moderate or severe intensity		X	X
	Gait disturbance independent of feelings of dizziness AEs		X	X
Tier 3	Specific AEs, SOCs or PDLCs ^a (incidence <7% of participants in all treatment groups)			X
	Change from baseline results (Labs, ECGs, Vital Signs)			X

AE=adverse event, CI=confidence interval, ECG=electrocardiogram, PDLC=Pre-Defined Limit of Change, SOC=System Organ Class, X=results will be provided

^aIncludes only those endpoints not prespecified as Tier 2 endpoints.

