8.4.7 Events of Clinical Interest

Selected serious and nonserious AEs are also known as ECIs and must be reported to the Sponsor.

Events of clinical interest for this study include:

- 1. Elevated AST $\geq 3x$ ULN
- 2. Elevated ALT $\ge 2x$ ULN or twice the baseline value
- 3. Elevated total bilirubin >2x ULN with ALP <2x ULN

4. AEs of dizziness that are rated by the investigator as being moderate or severe in intensity.

- 5. AEs related to gait disturbance, independent of feelings of dizziness.
- 6. Suicidal ideation and/or behavior or any self-injurious behavior reported as an AE.
- 7. QTcF interval meeting either of the criteria specified for study intervention discontinuation (Section 7.1).

Note that the above AEs and QTcF criteria are classified as ECIs only after the first dose of study intervention is administered. Sites should refer to the study ECI guidance document for details on assessment and follow-up, including follow-up on elevated liver function tests that met ECI criteria as assessed at Visit 10.

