9.9.2 Sample Size and Power for Safety Analyses

Table 11 and Table 12 summarize the percentage point differences between 2 treatment groups for a variety of hypothetical underlying incidences of AEs. These calculations assume (1) 56 participants in the MK-1942 daily dose group and 56 participants in the placebo group (Table 11) and (2) 28 participants in the MK-1942 intermittent dose group and 56 participants in the placebo group (Table 12). The calculations are based on a 2-sided 5%

PRODUCT: MK-1942
PROTOCOL/AMENDMENT NO.: 006-03

α-level and the method proposed by Miettinen and Nurminen [Miettinen, O. and Nurminen, M. 1985]; no multiplicity adjustments are considered.

Table 11 Differences (95% CIs) in Incidence in AEs Between MK-1942 Daily Dose and Placebo

Incidence of Adverse Event		Risk Difference	
MK-1942 Daily Dose (%)	Placebo (%)	Percentage Points	95% CI ^a
10.7	5.4	5.4	(-5.5, 17.0)
14.3	5.4	8.9	(-2.4, 21.3)
19.6	5.4	14.3	(2.2, 27.4)
14.3	10.7	3.6	(-9.3, 16.7)
19.6	10.7	8.9	(-4.7, 22.8)
25.0	10.7	14.3	(0.0, 28.7)
19.6	14.3	5.4	(-8.9, 19.7)
25.0	14.3	10.7	(-4.2, 25.6)
30.4	14.3	16.1	(0.6, 31.3)

AE=adverse event, CI=confidence interval

Incidences presented here are hypothetical and do not represent actual AEs in either group.

Table 12 Differences (95% CIs) in Incidence in AEs Between MK-1942 Intermittent Dose and Placebo

Incidence of AE		Risk Difference	
MK-1942 Intermittent Dose (%)	Placebo (%)	Percentage Points	95% CI ^a
10.7	5.4	5.4	(-6.3, 22.6)
14.3	5.4	8.9	(-3.6, 26.9)
21.4	5.4	16.1	(1.9, 35.0)
14.3	10.7	3.6	(-10.5, 22.1)
21.4	10.7	10.7	(-4.9, 30.2)
25.0	10.7	14.3	(-2.1, 34.0)
21.4	14.3	7.1	(-9.2, 27.0)
25.0	14.3	10.7	(-6.3, 30.9)
28.6	14.3	14.3	(-3.4, 34.6)

AE=adverse event, CI=confidence interval

Incidences presented here are hypothetical and do not represent actual AEs in either group.

 a Based on Miettinen and Nurminen method with 28 participants in the MK-1942 intermittent dose group and 56 in the placebo group using a 2-sided 5% α level.

^a Based on Miettinen and Nurminen method with 56 participants per treatment group using a 2-sided 5% α level.

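### Five of the seven events of clinical interest (liver, QTcF, suicidality) get a between-group 95% CI only if some arm reaches 7%, so they can be reported with no planned upper bound on excess risk

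*Combined protocol and SAP*

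**What the plan says.** Section 9.6.2 has no Tier 1 events, on the grounds that "the evaluation of safety and tolerability is focused on estimating rather than testing treatment differences" and that "the incidence of AEs of special interest is anticipated to be rare".

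An event enters Tier 2, and so gets a 95% CI against placebo, if at least 7% of any one arm has it: 4 participants on daily dosing, 2 on intermittent dosing or 4 on placebo. The threshold is justified by the statement that the CI for the "between-group difference in percent incidence will always include zero when treatment groups of equal size each have less than 4 events", with a matching statement for fewer than 2 events in the half-size arm; the section concludes that such an interval would contribute little. It also says that the intervals are descriptive and unadjusted for multiplicity.

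Some endpoints are Tier 2 at any count: five broad AE categories (including serious AEs and discontinuation due to an AE), moderate or severe dizziness, and gait disturbance independent of dizziness. Everything else is Tier 3: "Only point estimates by treatment group are provided for Tier 3 safety parameters". C-SSRS treatment-emergent ideation and behavior "will be considered as either Tier 2 or Tier 3 events, depending on the number of participants with an event observed within each treatment group".

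Section 8.4.7 lists seven ECIs: AST, ALT, total bilirubin with ALP, moderate or severe dizziness, gait disturbance, suicidal or self-injurious events reported as AEs, and "QTcF interval meeting either of the criteria specified for study intervention discontinuation".

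**The concern.** The section says it is estimating, then uses non-significance to decide which estimates get an interval. A CI that includes zero still says how large an excess the data allow. For an uncommon harm in arms of 56 and 28, that upper limit is most of what the trial can say.

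The SAP does not hold to its own reasoning throughout. Serious AEs, dizziness and gait disturbance keep their CI at any count. No reason is given for treating the AST, ALT, bilirubin, QTcF and suicidality ECIs differently. Safety is a primary objective (Section 3), and transaminase rises in earlier studies led to added laboratory monitoring here (Section 4.3.2). A result such as 3/56 v 0/56 on the ALT criterion could appear as 5.4% v 0% with nothing planned to show the excess still compatible with it.

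**Working it through.** **Inputs.** Arm sizes 56 (daily), 28 (intermittent) and 56 (placebo), and the Miettinen-Nurminen method at two-sided 5%, from Section 9.9.2. Tier 2 cut of 4, 2 or 4 participants, from Section 9.6.2. True incidences are assumptions; the documents give none for these events.

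**Method.** The limits are the values d that solve Z(d) = ±1.96, where

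Z(d) = (x1/n1 − x2/n2 − d) / √{[p1(1−p1)/n1 + p2(1−p2)/n2] × N/(N−1)},

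N = n1 + n2, and p1, p2 are the maximum likelihood estimates under p1 − p2 = d.

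**Step 1: reproduce the plan's figures.** All 18 intervals in Tables 11 and 12 are recovered to rounding. For example, 11/56 v 3/56 gives 2.19 to 27.38 (printed 2.2 to 27.4), and 6/28 v 3/56 gives 1.88 to 34.95 (printed 1.9 to 35.0).

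**Step 2: check the reason for the cut.** It holds at the planned sizes. The largest imbalances below the cut include zero and the first at the cut exclude it:

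| Active v placebo | 95% CI (points) |
|---|---|
| 3/56 v 0/56 | −1.3 to 14.7 |
| 4/56 v 0/56 | 0.4 to 17.0 |
| 1/28 v 0/56 | −3.1 to 17.8 |
| 2/28 v 0/56 | 0.3 to 22.8 |

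**Step 3: upper limits left unreported, against 0/56 placebo.**

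| Arm | Count | Upper limit (points) |
|---|---|---|
| Daily | 0/56 | 6.5 |
| Daily | 2/56 | 12.2 |
| Daily | 3/56 | 14.7 |
| Intermittent | 0/28 | 12.2 |
| Intermittent | 1/28 | 17.8 |

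The zero-count rows can be checked by hand. With no events, the constrained estimates at the upper limit are p2 = 0 and p1 = d, so d/(1−d) = 1.96² × N / [n1(N−1)]. For 56 v 56 this is 3.8416 × 112/(56 × 111) = 0.0692, so d = 6.5%. For 28 v 56 it is 3.8416 × 84/(28 × 83) = 0.1388, so d = 12.2%.

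**Step 4: how often no CI is produced.** One arm at 7% is enough for Tier 2, so every arm must stay below its cut. With placebo incidence near zero and the same true incidence p in both active arms,

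P(no CI) = P(X ≤ 3 | 56, p) × P(X ≤ 1 | 28, p).

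| p | Daily below cut | Intermittent below cut | No CI |
|---|---|---|---|
| 3% | 0.913 | 0.795 | 73% |
| 5% | 0.693 | 0.588 | 41% |
| 8% | 0.335 | 0.333 | 11% |
| 10% | 0.176 | 0.215 | 4% |

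If placebo also has 5%, the 5% row is multiplied by another 0.693: 0.408 × 0.693 = 28%.

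**The case against.** The strongest reply is that nothing is lost. Tier 3 events are still reported by arm, and the interval is a fixed function of counts and denominators, so anyone can compute it. No test, estimand or decision rule changes. That stands, and it is why this is an improvement rather than an error. It does not explain why the SAP should leave the calculation to the reader for events it has itself singled out.

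A second reply is that the cut is a minimum-count screen meant to limit the number of unadjusted intervals. That is reasonable for unspecified AE terms. It also disposes of one stronger reading, that the rule amounts to a significance filter. Falling below the cut coincides with non-significance only against 0/56: 4/56 v 1/56 is Tier 2 with a CI of −3.2 to 15.5, and 8 of the 9 intervals in Table 12 include zero.

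Third, serious cases may be caught elsewhere. Serious AEs and discontinuations due to AEs always get a CI; the QTcF ECI is itself a discontinuation criterion; C-SSRS results are also summarized in 11 categories; and the siDMC sees unblinded safety data. This is partial cover: an aggregate does not bound a particular ECI.

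Two further inferences are tempting and unsupported. One is that all these ECIs will probably land in Tier 3. The remark about rarity explains the absence of Tier 1 events and is not tied to the Section 8.4.7 list, which includes moderate or severe dizziness and an ALT criterion of twice baseline that needs no breach of the ULN. The documents give no expected incidence, and suicidal ideation may well not be rare in this population. The other is to read a single arm's chance of staying below the cut (69% for the daily arm at 5%) as the chance of no CI; any other arm can trigger it.

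**Conclusion.** The point holds in limited form. The plan withholds an interval because it would include zero, in an analysis it calls estimation, and leaves five of its seven ECIs subject to that rule. Those events can therefore be reported as counts and percentages with no planned upper bound, when the data remain compatible with an excess of 6.5 to 14.7 points (daily) or 12.2 to 17.8 points (intermittent) against 0/56 placebo. Any ECI that reaches 7% in any arm does get its CI.

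How often the gap would arise depends on incidences that the documents do not give. It is common at 3% to 5% in both active arms (73% to 41% with placebo near zero, 28% at 5% in all three arms) and uncommon at 8% to 10% (11% to 4%). The figures assume independent arms and treated numbers equal to those planned. A reader might conclude that the SAP equates a missing CI with safety, or that its threshold is miscalculated. It says no such thing about safety, and the threshold is correct. The liver findings described in Section 2.2.2 arose at 50 mg bid, with one case still blinded between placebo and that dose; this trial's maximum is 20 mg bid. That tempers urgency but does not remove the case for reporting the bound.

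**What to change.** In Section 9.6.2 and Table 7, list as Tier 2 at any count:

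- the AST, ALT and total-bilirubin/ALP ECI criteria;
- the QTcF ECI criteria;
- ECI 6 as Section 8.4.7 defines it, so including self-injurious behavior and limited to events reported as AEs;
- as separate rows, because they are different endpoints, C-SSRS treatment-emergent ideation and C-SSRS treatment-emergent behavior.

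Report the Miettinen-Nurminen 95% CI for each active arm against placebo, including when both counts are zero. Delete the clause that makes the C-SSRS tier depend on the count. Keep the 7% rule for all other AE terms and PDLCs.

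The cost is a few rows in one table and one output, with no new data, no effect on alpha and no change to clinical management. The downside is a few more wide, unadjusted intervals in the CSR, which the SAP already labels descriptive.
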